- c) **Confidentiality** will be preserved by use of ID code numbers for identification. ID and name associations will be password protected in an encrypted master file to which only the PIs and the statistician will have access. Randomization procedures were discussed previously. Participant data, including computer data disks, will be kept in a locked room. Identifying information about a subject will not be used during the discussion or presentation of any research data. To ensure confidentiality and anonymity during the study, each subject will be assigned a confidential study number. Access to the subject study identification codes or other information will be restricted to the PIs, co-investigators, and study staff, and upon written request, to the Institutional Review Board (IRB) or other regulatory agencies, or by written request of the subject, released to others. Paper records will be stored in locked file cabinets in the investigators' offices, and all computers used for data management and analysis will be password-protected and located in secure offices.
 - i) Participants will be recorded as they walk on the gait mat. No sound will be recorded. The videos will not be destroyed. The tapes will be used by the research team to score the evaluations and refine measurements already collected. Participants will not receive any monetary compensation for being taped.

8) Data Analysis: Study outcomes will be assessed at baseline, month 2, 4, immediate post-intervention (month 6), and month 9. Attendance rates will be reported. The purpose of the analyses are to estimate effects that can be used for a larger confirmatory study.

- a) **Aim 1:** Linear mixed effects models will be used to compare the trajectories of composite EF score at baseline and months 2/4/6/9. The optimal treatment period that yields the greatest treatment effect will

be identified. Estimates with 95% CI of dance effects at different time points as well as slope of change will be reported. The analysis will also be applied to **individual EF tests** to examine whether the dance effects differentiates among different aspects of EF.

- Pre-specified covariates¹¹⁵⁻¹¹⁷ to account for **confounding** include age, gender, education and chronic illnesses.¹¹⁸ Baseline distribution of covariates will be compared to assess adequacy of randomization. We do not discount residual/unmeasured confounding – though this is more of an issue in observational studies without randomization.
- **Intensity** (*actigraphy in-session*) and **dose** (*number of sessions*) of dance and walking will also be examined.

Power: The pilot sample size was based on pragmatics of recruitment and necessities for examining feasibility.¹¹⁹ Based on previous studies, we expect correlations of at least 0.80 between repeated EF scores. With 16 in each group and assuming 20% drop out rate at post intervention, we can detect a difference of 0.075 SD per month in EF slope using measurements at baseline/2/4/6 months, between groups with 80% power using 2-sided tests with alpha level 0.05.

- b) **Aim 2:** The comparison of imaging measures pre-post intervention (month 0 vs. 6) between study arms will be analyzed using multivariate covariance-based analyses, adjusting for age, gender and other covariates. Multivariate covariance-based analyses are particularly sensitive to detecting effects in the presence of between-subject variability and collinearity– issues particularly important to consider in aging populations and with neuroimaging data. Drs. [name] and [name] have considerable experience with these neuroimaging analyses.^{96, 120-127} Mean and confidence intervals of imaging measures within each group as well as the difference between the two groups will be reported for performance at each time point of pre and post intervention, and for change at post from pre intervention.

- **fMRI: WWT imagery task, DSST and Flanker Task.** Standard pre-processing and first-level analyses will be performed with SPM12 (see Equipment). **Group-Level Covariance Analyses.** Ordinal Trend Covariance Analyses (OrT-CVA; http://www.nitrc.org/projects/gcva_pca) will be used to analyze the imagined WWT, DSST and Flanker Tasks^{128, 129}. OrT-CVA will be used to identify covariance patterns in the fMRI signal as a function of trial type (iT, iW and iWWT on the imagined WWT, task and rest blocks on the DSST, incongruent and congruent trials on Flanker Task) at each study visit (pre and post-intervention). OrT-CVA employs a PCA to the data matrix that is then transformed to a matrix of the experimental design. Linear regression is then applied to detect a covariance pattern (ordinal trend) in the fMRI signal as a function of task conditions that is based on a linear combination of a small set of principal components. An ordinal trend is a monotonic change in pattern expression as a function of task conditions, in this case as a function of trial type (iW, iT & iWWT). The expression of an ordinal trend is quantified in terms of a participant-specific expression score that is derived by projecting the covariance pattern onto a participant's scan for each task condition. Each intervention group will be split into two, and split half-reliability assessed by correlations on imaging measures.

Power: The sample of 16 per group is within the number recommended to conduct reliability studies¹³⁰ and to improve study design.¹³¹ We will report estimates of imaging measures to improve study design of our full scale RCT.

- c) **Potential pitfalls and solutions.** We recognize that despite all our efforts, there will be **missing data**. To address this issue we will identify contact persons. Flexible scheduling with makeup sessions is provided. We will not restrict participation in **outside activities** keeping with the pragmatic nature of the trial. We will track outside activities using validated leisure and activity scales (see Table 1) to see if it will explain durability of any observed effects.

9) Data quality control and database management

- a) The content captured will consist of demographics, medical history, MRIs, laboratory data, clinical and biological safety outcomes and adherence data. Data management will incorporate the expertise of the Research Informatics Core (RIC), a component of the Einstein-Montefiore Institute for Clinical and Translational Research (ICTR) consisting of developers and database analysts who specialize in the management of research data. REDCap (Research Electronic Data Capture) is a mature, secure, web-based application for building and managing online surveys and databases developed by Vanderbilt

University to support the electronic collection and management of clinical research data. It has been available at Einstein-Montefiore since it became REDCap consortium member in 2010.

REDCap can be used to collect virtually any type of data (including 21 CFR Part 11 and FISMA-compliant environments), but it is specifically geared to support online or offline data capture for research studies and operations, being by design HIPAA-compliant. REDCap's streamlined process for rapidly developing projects helps to create and design projects using 1) the online method from a web browser using the Online Designer; and/or 2) the offline method by constructing a 'data dictionary' template file in Microsoft Excel, which can be later uploaded into REDCap. Both surveys and Data Collection Forms (or a mixture of the two) can be built using these methods. REDCap provides an intuitive interface for users to enter data and have real time validation rules (with automated data type and range checks) at the time of entry. This system offers easy data management with audit trails for reporting, monitoring and querying participant records. REDCap provides automated export procedures for seamless data downloads to Excel and common statistical packages (SPSS, SAS, Stata, R), as well as a built-in project calendar, a scheduling module, ad hoc reporting tools, and advanced features, such as branching logic, file uploading, and calculated fields.

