Aim 2: Explore functional and structural neuroplasticity for cognitive benefits of social dancing in seniors at risk for dementia. We will explore neuroplasticity in functional activation/deactivation and structural connectivity patterns as a function of social dancing (pre-post intervention). We will use **functional Magnetic Resonance Imaging (fMRI)** to investigate neuroplasticity in functional activation/deactivation patterns with our validated 'imagined WWT' task³²- as well as with DSST and Flanker tests, which are responsive to physical interventions.²⁵ *We predict that compared to walking, dancing will result in greater intervention-related changes in functional activation of supplementary motor, anterior cingulate and prefrontal regions during imagined WWT, DSST and Flanker tests.*

To investigate neuroplasticity in structural connectivity patterns, we will use **diffusion-weighted imaging**, which are responsive to social dancing and physical interventions.^{33, 34} We predict that compared to walking, dancing will result in greater intervention-related changes in structural connectivity patterns, including fornix and cingulum.

Social dancing appeals to older adults, has intrinsic value, is enjoyable, and has high potential for sustainability. This R21 proposal is novel and high risk, but will provide the evidence base to develop a

definitive full-scale RCT to support or refute prescription of social dancing to prevent cognitive decline in older adults at high risk of AD and related dementias.

2) Study Design

Overview and Design. We propose a pilot single blind RCT of social dancing versus walking in 32 dementia at-risk seniors (16/group). For Aim 1, outcome is change in EF composite score measured with a comprehensive battery of conventional (DSST), computerized (Flanker test) and cognitive-motor (WWT) EF tests assessed at baseline, month 2, month 4, month 6 (immediate post-intervention), and 3 months post-intervention to derive trajectories to inform design of future R01. Feasibility is assessed through metrics described in Table 1. For Aim 2, outcome is neuroplasticity measured using our *validated fMRI iWWT protocol, DSST and Flanker Tests, and white matter integrity*.

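### The Aim 1 EF model states neither a common month 0 mean nor baseline EF adjustment and leaves the visit effect undefined; fixing this narrows the intervals by about 4–5% at no cost

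*Combined protocol and SAP*

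**What the plan says.** All references are to the combined protocol and SAP.

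- **Model** (section 8, a) Aim 1): "Linear mixed effects models will be used to compare the trajectories of composite EF score at baseline and months 2/4/6/9". Month 0 is therefore one of the responses. The fixed effects are not written out.
- **Reported estimates** (same place): "Estimates with 95% CI of dance effects at different time points as well as slope of change will be reported". The text does not say whether a visit effect is the arm difference at that visit or the arm difference in change from month 0.
- **Covariates** (same place): those pre-specified "include age, gender, education and chronic illnesses". Baseline EF is not among them.
- **Outcome** (section 2, Overview and Design): "For Aim 1, outcome is change in EF composite score measured with a comprehensive battery".
- **Expected correlation** (section 8, a) Aim 1, Power): "we expect correlations of at least 0.80 between repeated EF scores".
- **Purpose** (opening of section 8): "The purpose of the analyses are to estimate effects that can be used for a larger confirmatory study".

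Randomization (section 2c) is stratified by gender and age, not by EF.

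**The concern.** Randomization implies that the two arms share one expected EF score at month 0. A model that does not use this fact estimates a month 0 arm difference that is known to be zero in expectation, and every reported effect pays for it. A raw visit difference contains most of the chance baseline imbalance. A difference in change over-corrects for it, because part of any imbalance regresses to the mean. A model with a common month 0 mean, or with baseline EF as a covariate, removes it in expectation.

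The plan does not say which of these will be fitted. With 16 per arm the chance imbalance is not negligible. The visit and slope estimates with their intervals are what Aim 1 hands to the larger trial, and the same visit estimates are to be used to pick the best treatment duration.

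**Working it through.** **Inputs from the plan.** n = 16 per arm; visits 0/2/4/6 for power; 20% dropout by post-intervention; r = 0.80; detectable slope difference 0.075 SD per month at 80% power, two-sided 0.05.

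**Assumptions added here.** Constant correlation between visits (compound symmetry), SD 1 at each visit, no gain from stratification or covariates, normal approximation. Dropout means 12.8 per arm have month 6 and 3.2 have months 0, 2 and 4 only.

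**1. The plan's own figure.** For months 0/2/4/6, Sxx = 20. With a separate intercept per arm and complete data, SE(slope difference) = √[2(1 − r)/(n·Sxx)] = √[0.4/320] = 0.0354. The detectable difference is (1.96 + 0.84) × 0.0354 = 0.099 SD per month. It is 0.105 with month 6 missing in 20%, and 0.111 with only 12.8 per arm. The stated 0.075 is not reproduced. That is a separate matter: a common month 0 mean gives 0.094, 0.100 and 0.105 respectively, so it does not close the gap.

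**2. Month 6 effect, r = 0.80, 20% missing month 6.**

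- The squared multiple correlation of month 6 on months 0, 2 and 4 is R² = 3r²/(1 + 2r) = 1.92/2.6 = 0.738.
- Raw difference: variance = 2[(1 − R²)/12.8 + R²/16] = 0.1332; SE 0.365.
- Difference in change: 0.1332 + 2/16 − 2r(2/16) = 0.1332 + 0.125 − 0.200 = 0.0582; SE 0.241.
- Common month 0 mean: 0.1332 − r²(2/16) = 0.1332 − 0.080 = 0.0532; SE 0.231.

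| Contrast at month 6 | SE | 95% half-width | Narrowing from common month 0 mean |
|---|---|---|---|
| Common month 0 mean | 0.231 | 0.452 | – |
| Difference in change | 0.241 | 0.473 | 4% |
| Raw visit difference | 0.365 | 0.715 | 37% |

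**3. Slope, months 0/2/4/6, same missing data.** Generalised least squares gives SE 0.0376 with a free month 0 difference and 0.0358 with a common mean: 1 − 0.0358/0.0376 = 5% narrower.

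**4. Other correlations, change contrast at month 6.**

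| r | SE, change | SE, common mean | Narrowing |
|---|---|---|---|
| 0.50 | 0.380 | 0.337 | 11% |
| 0.80 | 0.241 | 0.231 | 4% |
| 0.90 | 0.171 | 0.167 | 2% |

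**5. How much baseline imbalance reaches the estimate.** The chance month 0 difference has SD √(2/16) = 0.354. The plan's 0.075 per month is 0.45 SD over six months, and P(|imbalance| ≥ 0.45) = 2[1 − Φ(1.27)] = 0.20. Given an imbalance d, at r = 0.80:

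- the raw visit difference shifts by r·d = 0.80d, so 0.36 SD for d = 0.45;
- the change contrast shifts by −(1 − r)d = −0.20d, so −0.09 SD for d = 0.45;
- the slope with complete data has visit weights −0.15, −0.05, 0.05 and 0.15, so it shifts by −0.15d + 0.80d(0.15) = −0.03d, or −0.0135 SD per month for d = 0.45.

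**The case against.** A reader might infer that the plan has chosen a free month 0 arm difference. It has not. It writes out no fixed effects, so the loss of precision depends on how the model is fitted. That stands, and the point is worded accordingly. The text nevertheless admits the conventional fit and names neither remedy.

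A reader might also take the 37% figure, or the one-in-five chance of a 0.45 SD imbalance, as the size of the problem. The documents do not support that. The design overview defines the outcome as change, the analysis section compares trajectories and slopes, and the power statement is about slope. On those contrasts month 0 EF is already largely used: at r = 0.80 the SE falls from 0.365 to 0.241 without any constraint, and the common mean adds only the step to 0.231. A 0.45 SD imbalance moves the month 6 change effect by 0.09 SD, not by 0.45.

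Three further points stand. Neither contrast is biased over repeated randomizations. The plan says at least 0.80, so for the composite 4–5% is near the upper end of the gain. Stratification and the listed covariates give some protection: if they explained 20–30% of EF variance (an assumption), the imbalance SD would be about 0.32–0.30 and the 20% chance about 15–13%.

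The constraint also has a condition. Section 2c randomizes at the initial visit, participants are not blinded, and the order of month 0 testing and disclosure of allocation is not stated. A common mean is safe only if testing comes first.

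**Conclusion.** The point holds as a modest, free improvement. The plan sets no common month 0 mean, does not list baseline EF as a covariate and does not define the visit effect. A conventional fit of that text remains valid on average, but gives estimates that depend on the realised baseline imbalance and intervals about 4% (month 6 change) to 5% (slope) wider than the better model would at r = 0.80. Individual EF tests may have lower correlations than the composite, and there the gain is larger.

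The large loss arises only if visit effects are reported as raw arm differences. The text does not rule that out, which is a reason to define the contrast, but it points the other way. The figures rest on compound symmetry, unit SD and no gain from stratification or covariates.

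**What to change.** In section 8, a) Aim 1, specify visit as a factor, one month 0 mean for both arms, and arm-by-visit terms from month 2 on, using all available visits. Modelling post-baseline EF with baseline EF as a covariate is equivalent in large samples. Apply the same rule to the slope model and to the individual EF tests. Define the dance effect at each visit, and the slope, as the terms from these models.

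State that month 0 testing is completed before participants learn their allocation.

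The cost is a few lines of specification and, if not already practice, that ordering of the initial visit. No new data are needed.

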Recruitment	Analyze recruitment sources by PI.	Monitor to improve recruitment rates and identify barriers.
Implementation	Proportion completed successfully. Observe all phases to find bottlenecks	Compare completion rates by education. Testers feedback on non-completion and other barriers to develop solutions.
Retention	Retention rates to be reported. 20-25% attrition common in high-risk samples.	Dancing program implemented in frailty and dementia. ^{6, 15, 78-82} Make-up sessions provided. Transportation and snacks will be provided. Dose/frequency accounted in analyses. Compensation at \$10/session consistent with IRB guidelines, and has been reported to promote adherence in exercise programs. ⁸³
Safety	Staff monitoring/DSMB oversight	DSMB and safety procedures
Practicality	PI, staff and subject observations	Extent to which intervention can be done with available resources
Acceptability	Post-study interviews of participants	Help refine RO design and enhance generalizability
Reporting	Report pilot study design and results	CONSORT guidelines will be followed: See ref ⁸⁴ for details.

- f) **OUTCOME Aim 2 (Neuroplasticity):** Encouragingly, pilot dance intervention trials have shown neuroplasticity with similar or smaller samples (12 to 48) over 6-months or less,^{3, 85-89} including the FAST study³⁴. Our primary neuroimaging measure is task-based fMRI because functional brain changes are a more sensitive biomarker of AD than gray matter volume. Our exploratory neuroimaging measure is DTI because it has been shown to be sensitive to aerobic exercise³³ and social dancing intervention.^{34, 90} Furthermore, functional and structural changes may occur before the emergence of cognitive symptoms in dementia.⁹¹⁻⁹⁵

- i) **Task-Based fMRI (Primary):** We will examine functional activation/deactivation changes pre-post intervention in both groups during an imagined WWT (iWWT) protocol developed by our group.³²

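### The stated detectable slope difference of 0.075 SD per month does not follow from the plan's own inputs, which give about 0.11 SD per month and roughly 50% power at 0.075

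*Combined protocol and SAP*

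**What the plan says.** The power statement is in section 8, Data Analysis, under Aim 1. It first says the sample size rests on practical recruitment and feasibility, and then gives a numerical claim. The inputs are:

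- Correlation: "we expect correlations of at least 0.80 between repeated EF scores".
- Size and dropout: "With 16 in each group and assuming 20% drop out rate at post intervention".
- Result and visits: "we can detect a difference of 0.075 SD per month in EF slope using measurements at baseline/2/4/6 months".
- Test: "between groups with 80% power using 2-sided tests with alpha level 0.05".

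No formula, covariance structure or random-slope variance is given. The analysis paragraph just above it is wider than the power statement: "Linear mixed effects models will be used to compare the trajectories of composite EF score at baseline and months 2/4/6/9". The retention row of the feasibility table in section 2(e) notes "20-25% attrition common in high-risk samples", so 20% dropout is the favourable end of the plan's own range.

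**The concern.** A reader can work out the slope difference directly from these inputs, and the result is well above 0.075. This is the only numerical power claim in the plan; the Aim 2 power paragraph gives no figure. It tells readers that the pilot has an 80% chance of detecting 0.075 × 6 = 0.45 SD over the six-month intervention. If the real chance is about one half, a non-significant slope says much less against a moderate effect than the plan suggests. The pilot exists to inform a larger trial, so the error could mislead that planning, particularly if the same calculation were reused to size it.

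**Working it through.** **Inputs, all from the Aim 1 power statement.** 16 per arm; 20% dropout by month 6; correlation ρ = 0.80; visits at 0, 2, 4 and 6 months; two-sided α = 0.05; 80% power; outcome in SD units, so the total variance is 1.

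**Assumption.** The correlation is the same for every pair of visits and true slopes do not vary between people. The plan gives no structure. This choice is favourable, because random slopes or a correlation that decays from 0.80 would lower the power.

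**Step 1: variance of one person's slope.** The within-person variance is 1 − ρ = 0.20. The visit times have mean 3, so their sum of squared deviations is 9 + 1 + 1 + 9 = 20. The slope variance is 0.20/20 = 0.01, an SD of 0.100 per month.

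**Step 2: standard error of the difference between arms.**

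- Completers only: 16 × 0.8 = 12.8 per arm, so SE = √(2 × 0.01/12.8) = 0.0395.
- Dropouts miss month 6 only: visits 0, 2 and 4 have a sum of squares of 8, so the average is 0.8 × 20 + 0.2 × 8 = 17.6 and SE = √(2 × 0.20/(16 × 17.6)) = 0.0377.

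**Step 3: detectable difference and power.** The multiplier is 1.960 + 0.842 = 2.802. Power at 0.075 is Φ(0.075/SE − 1.960).

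| Case (ρ = 0.80, months 0/2/4/6) | Detectable slope, SD/month | Over 6 months, SD | Power at 0.075 |
|---|---|---|---|
| Plan's statement | 0.075 | 0.45 | 80% |
| 12.8 completers per arm | 0.111 | 0.66 | 47% |
| 16 per arm, 20% missing month 6 only | 0.106 | 0.63 | 51% |
| As above, arms constrained to a common baseline | 0.100 | 0.60 | 55% |
| No dropout | 0.099 | 0.59 | 56% |
| No dropout, common baseline | 0.094 | 0.57 | 61% |
| 25% attrition, 12 completers per arm | 0.114 | 0.69 | 45% |

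The two no-dropout rows are more generous than the plan's inputs and still miss 0.075. Using t in place of normal quantiles with 12.8 per arm makes it slightly worse (0.116; 44%). A one-sided test gives 0.098 with 12.8 per arm and 0.088 with 16. A simple change from month 0 to month 6 gives 0.117, and the same comparison adjusted for baseline gives 0.111, both with 12.8 per arm.

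**Step 4: other correlation structures (12.8 per arm).** If 0.80 is the lowest correlation, at the six-month gap, with higher values between closer visits under first-order decay, the detectable difference is 0.117 and power at 0.075 is 44%. If 0.80 applies to adjacent visits and decays from there, the figures are 0.182 and 21%.

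**Step 5: what would give 0.075.**

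- Solving for correlation: 1 − 20 × (0.075/2.802)² × 12.8/2 = 0.908 for completers, and 1 − 17.6 × (0.075/2.802)² × 16/2 = 0.899 when only month 6 is missing.
- Solving for size at ρ = 0.80: n = 2 × 7.849 × 0.01/0.075² = 27.9, so 28 completers per arm, or 28/0.8 = 35 randomized per arm.
- Adding month 9: the sum of squares rises to 48.8, and 12.8 completers per arm give 0.071 with 84% power (0.074 and 81% with t quantiles).

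Each of these changes an input that the sentence states.

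**The case against.** The strongest reply is that 0.80 is given as a lower bound. A correlation of 0.90 satisfies it, and with 20% missing only month 6 it gives 0.0747 and 80.4% power. The sentence might also mean 0.80 for a single test, with the composite correlating more highly. If each of three tests has retest correlation 0.80 and the inter-test correlation is r both within and across visits, the composite's correlation is (2.4 + 6r)/(3 + 6r). That is 0.875 at r = 0.3, 0.90 at r = 0.5 and 0.909 at r = 0.6. These values of r are assumptions; the plan gives none.

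This shows that the figure could come from an input left unstated. It does not make the sentence right as written. A power claim resting on a minimum correlation has to hold at that minimum, and 0.80 is the only value given. Going from 0.80 to 0.90 halves the within-person variance, so the difference is not one of rounding.

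Month 9 is in the planned mixed model and would bring the figure close. But the power statement specifies "using measurements at baseline/2/4/6 months", and month 9 falls three months after the intervention ends, where a straight-line continuation is not assured.

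Two points on consequence do stand. The sample size does not depend on this figure, and the stated purpose of the analysis is estimation with 95% confidence intervals, which would show the imprecision in any case. Also, multiplying the slope by six assumes linear change, while Aim 1 expressly looks for a plateau, so the six-month figures apply only under linearity.

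**Conclusion.** The concern holds. At the plan's own inputs the detectable slope difference is 0.106 to 0.111 SD per month, about 1.4 to 1.5 times the stated 0.075, and power at 0.075 is about 47% to 51% instead of 80%. The range reflects how the 20% dropout is applied. The result assumes an equal correlation of 0.80 and no variation in true slopes, which favours the plan. None of the analyses tried with the stated inputs reached 0.075. Where that figure came from cannot be told from the documents. The error affects how the pilot's precision is described and how a null slope might be read; it does not affect the design, the sample size or the planned estimates.

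**What to change.** Restate the Aim 1 power sentence: with 16 per arm, 20% dropout by month 6, an equal correlation of 0.80 and visits at months 0, 2, 4 and 6, the trial has 80% power for a slope difference of about 0.11 SD per month (about 0.65 SD over six months if change is linear), and about 50% power for 0.075. If a correlation near 0.90 was used, give that value and its source in place of the 0.80 minimum, and say whether it refers to the composite or to single tests. In either case, name the covariance structure and say how dropout enters the calculation.

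The cost is one or two sentences and a less favourable stated detectable effect. No additional participants, visits or analyses are needed.

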The iWWT is strongly correlated with actual WWT performance, and engages a distributed network of brain regions, including cerebellar, precuneus, supplementary motor and other prefrontal regions.³² The iWWT protocol involves 5 repeated blocks of imagined walking (iW), imagined talking (iT), and iWWT, and takes 12 minutes to administer. We will also examine functional activation/deactivation changes during DSST and Flanker tests. We will use a DSST task adapted for use in an fMRI environment and validated in older adults.⁹⁶ This task takes about 10 minutes and has 2 practice and 5 testing blocks, with 18 items each (total 95 test items). We will also use a Flanker task optimized for fMRI environment, with a 4-minute practice block and three 4-minute test blocks for a total of 120 test items (60 congruent, 60 incongruent) presented with jittered inter-stimulus intervals (4-8 sec).⁹⁷ *We predict that dance will increase activation in supplementary motor, anterior cingulate and other prefrontal cortex regions during the iWWT, DSST and Flanker tasks to a greater extent than walking.* We expect treadmill training to increase activation in the somatosensory cortex and the cerebellum. Jovancevic et al noted differences in activation in response to DSST on fMRI in 5 women (mean age 55) in the left middle frontal gyrus, right inferior parietal lobule, and left angular gyrus following a 6-week video dance program.⁹⁸

- ii) **Diffusion-Weighted Imaging (exploratory).** We propose to examine **pre-post changes in structural connectivity** as a function of social dancing. Structural changes in white matter integrity have been observed following physical and social dancing interventions.³⁴ Based on these initial findings, we propose to monitor structural changes in white matter integrity (fractional anisotropy) using Tracts Constrained by Underlying Anatomy (TRACULA).⁹⁹ *We expect that dance will change white matter integrity in fornix, cingulum and over frontal integrity to a greater extent than walking.*
- g) **Other measures:** We will collect other measures to explore the broader impact of dancing. Given R21 space limits, these measures are summarized in Table 1. We have administered 3-hour test batteries to over 3000 participants in our other aging studies with minimal attrition.

Table 1. Summary of secondary outcomes, covariates and process measures

Domains	Tests and procedures (refs)	Description (0,2,4,6, 9 months)	Time

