Clinical	Study clinician evaluation ^{35, 100} of neurological and musculoskeletal systems including gait	Standardized examination and CDR rating. Clinicians Global Impression of Change ^{101, 102}	30 m
Cognitive	Neuropsychological battery ¹⁰³	Test of multiple cognitive domains. ¹⁰³	60 m
	CHAMPS ¹⁰⁴	Lifestyle changes baseline and post-intervention	15 m
	Gait variables	GAITRite	10 m
	Balance	Unipedal stance, trunk sway (covariate)	5 m
	ADL scales	Monitor changes in function	5 m
Mood	Geriatric depression scale ¹⁰⁵	Depressive symptoms (covariate)	5 m

3) DATA AND SAFETY MONITORING PLAN:

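### Aim 2 does not name the month-0 imaging value as a covariate for the between-arm change; adding it is an optional, conditional gain in precision

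*Combined protocol and SAP*

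**What the plan says.** Aim 2 is about change. The Aim 2 statement predicts that "dancing will result in greater intervention-related changes in functional activation". Section 2(f) examines "functional activation/deactivation changes pre-post intervention in both groups" for task fMRI (the primary imaging measure) and "pre-post changes in structural connectivity" for diffusion imaging (exploratory).

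Section 8(b) analyses the month 0 versus month 6 comparison between arms by multivariate covariance-based methods, "adjusting for age, gender and other covariates". Means and confidence intervals, within arm and for the between-arm difference, are to be given for "performance at each time point of pre and post intervention, and for change at post from pre intervention".

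The covariates named elsewhere are those for Aim 1 in section 8(a), which "include age, gender, education and chronic illnesses", and the balance and depression measures that Table 1 marks as covariates. The eligibility section gives the pre-intervention MRI one further use, an exploratory split by brain pathology. No section names the month-0 value of an imaging measure as a covariate for its own change.

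**The concern.** A change score uses the month-0 value with a fixed coefficient of one. A regression that also includes the month-0 value estimates that coefficient, and in large samples its residual variance is never greater. Section 8 says the analyses are meant to estimate effects for a larger confirmatory study, so interval width is part of what this pilot delivers. The month-0 scan is collected anyway.

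The term covariance-based does not settle the matter. The fMRI paragraph of section 8(b) shows that it refers to ordinal trend covariance analysis, which extracts patterns of signal across task conditions. That is not analysis of covariance on the baseline value.

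At stake is the width of the adjusted Aim 2 intervals in a small trial.

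**Working it through.** Aim 2 states no power or precision figure, so there is nothing to reproduce first.

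**Inputs**
- 16 per arm (sections 2 and 8).
- 20% dropout, stated in the Aim 1 power paragraph and borrowed here: 16 × 0.8 = 12.8, taken as 13 per arm, N = 26.
- 95% level, stated for Aim 1 and borrowed here.
- Pre-post r and SDs of imaging measures: not in the documents. r is varied. Month-0 SD = 1 and month-6 SD = k, with k = 1 unless stated.
- One scalar score per participant on the same scale at both visits (assumption).
- Age and gender in both models.

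**Formulas**
- Change score: residual variance 1 + k² − 2rk, which is 2(1 − r) when k = 1.
- With the month-0 value added: k²(1 − r²), which is 1 − r² when k = 1.
- SE = √(2 × variance / 13 × f), where f = 1 + q/(23 − q) is the average small-sample cost of q covariates. The t quantile has 24 − q df.
- Change model: q = 2, f = 1 + 2/21 = 1.095, t(22) = 2.074. Adjusted model: q = 3, f = 1 + 3/20 = 1.150, t(21) = 2.080.

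**Example, r = 0.5, k = 1.** Change: variance 1.00, half-width 2.074 × √(2 × 1.00/13 × 1.095) = 0.851. Adjusted: variance 0.75, half-width 2.080 × √(2 × 0.75/13 × 1.150) = 0.758. Ratio 0.890.

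**Equal SDs** (half-widths in month-0 SD units; the last column is from 20,000 simulated trials per r with both models fitted)

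| r | Change | Adjusted | Ratio | Trials in which adjusted is narrower |
|---|---|---|---|---|
| 0.3 | 1.007 | 0.834 | 0.828 | 94% |
| 0.5 | 0.851 | 0.758 | 0.890 | 86% |
| 0.7 | 0.659 | 0.625 | 0.947 | 69% |
| 0.8 | 0.538 | 0.525 | 0.975 | 56% |
| 0.9 | 0.381 | 0.381 | 1.002 | 40% |
| 0.95 | 0.269 | 0.273 | 1.015 | 31% |

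**Break-even.** The fixed cost of the extra covariate is (2.080/2.074) × √(1.150/1.095) = 1.0275 in width, or 1.056 in squared width. The variance ratio is (1 − r²)/[2(1 − r)] = (1 + r)/2. Setting (1 + r)/2 = 1/1.056 gives r = 0.894. With no other covariate the break-even is 0.904. With all six covariates named anywhere in the plan, at one df each, it is 0.87.

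**Unequal SDs.** Change variance minus adjusted variance equals (1 − rk)². This is never negative and is zero at r = 1/k, so the loss cannot exceed the fixed cost of 2.75%, and for k above 1 it occurs in a band of r.
- k = 1.1: adjusted is wider only for r of about 0.75 to 0.97.
- k = 1.25: adjusted is wider only for r of about 0.61 to 0.90. At r = 0.8 the half-widths are 0.638 (change) and 0.656 (adjusted). At r = 0.95 they are 0.369 and 0.341, so adjustment gains again.
- k = 0.8 or 0.9: adjusted is narrower at every r.

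**The case against.** The covariate list is open, the change estimate is unbiased and imaging is a pilot aim, so it can fairly be said that no error has been shown. That stands, and it is why this is only an optional improvement.

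A second objection is that the plan specifies a pattern analysis and not a regression of a scalar. This stands in part. Fractional anisotropy by tract is a scalar. The fMRI analysis also yields a participant-level expression score, but one per task condition, and patterns are identified at each visit. If patterns are derived separately by visit, pre and post scores need not share a scale, and r and the SD ratio are then undefined. The widths above do not carry over to that case, and they also leave out error in estimating the pattern.

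Third, the planned pre, post and change summaries would let a later team recover r and an unadjusted version of the baseline-adjusted result, provided they cover the same completers. That is correct. The age- and gender-adjusted interval could not be recovered in this way.

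Fourth, the gain may be negligible. At r = 0.8 it is 2-3% on average, and in a single trial the adjusted interval is the narrower one only slightly more often than not. The plan's correlation of at least 0.80 is for executive function scores and does not tell us the imaging value.

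A reader might go further and infer that the plan rules out baseline adjustment, that the planned contrast is biased, or that adjustment always helps. The documents support none of these. The covariate wording is open, allocation is randomised, and the calculation shows ranges of r where adjustment loses slightly.

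**Conclusion.** The point holds as an optional gain in precision. Among the covariates the plan names, the month-0 imaging value is absent, though not excluded. With 13 completers per arm, the borrowed 95% level, a common-scale scalar score, equal SDs, and age and gender in both models, naming it would on average narrow the change interval materially at low to moderate r (about 17% to 11% for r of 0.3 to 0.5). The gain is slight at r = 0.8 and disappears near 0.89. The worst average loss is just under 3%, whatever the SD ratio. Because the documents give no imaging r or SD, the actual gain cannot be fixed within this range.

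**What to change.** State in section 8(b) that, for each scalar imaging measure, the between-arm effect and its confidence interval come from a regression of the month-6 value (or, equivalently for the arm effect, the change) on arm, the month-0 value of that measure, age and gender. Apply this to fractional anisotropy by tract. Apply it to fMRI expression scores where the pre and post scores come from one common pattern projected onto both visits, so that change is defined. The plan does not currently say whether that is so, and stating it is a separate specification decision. Keep the planned pre, post and change summaries as descriptive.

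The cost is one degree of freedom per model and, in the unfavourable ranges of r above, an interval wider by at most about 3% on average. No new scans are needed, and nobody who could contribute a change score is lost, because a change score already requires a usable month-0 scan.
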